Proprietary confidential information © 2021 Boehringer Ingelheim International GmbH or one or more of its affiliated companies

		Vital Signs (BP, PR, SaO ₂) ¹	
5:06	13:06	CANTAB RVP	
	13:13	Vital Signs (BP, PR, SaO ₂) ¹	██████████ right before CANTAB SWM
	13:17	CANTAB SWM	
	13:23	Vital Signs (BP, PR, SaO ₂) ¹ PK blood (ketamine) ¹	██████████ right before CANTAB PAL
	13:27	CANTAB PAL Review In-/ Exclusion Criteria	in the end of PAL, eligibility results will be displayed
	13:39	Questioning for AEs Vital Signs (BP, PR, SaO ₂)	
5:40	13:40	██████████	
	13:53	Vital Signs (BP, PR, SaO ₂)	
	13:54	██████████	
	13:57	██████████	
	14:00	Vital Signs (BP, PR, SaO ₂) ██████████	
	14:01	██████████	
	14:12	Vital Signs (BP, PR, SaO ₂)	
	14:13	██████████	
	14:19	Questioning for AEs	
6:20	14:20	██████████	
6:30 ¹	14:30 ¹	Vital signs (BP, PR, SaO ₂) ██████████ Stop of ketamine infusion ¹ Stop of continuous ECG and SaO ₂ monitoring	¹ can be prolonged for a maximum of 15 min, in case delays from PT occur for CANTAB, ██████████ or terminated earlier, if the above tests are completed (or any test drops out)
6:45	14:45	Vital Signs (BP, PR, SaO ₂)	
7:00	15:00	Questioning for AEs Vital Signs (BP, PR, SaO ₂) 12-lead ECG	
7:15	15:15	Vital Signs (BP, PR, SaO ₂)	
7:30 ¹	15:30 ¹	Questioning for AEs Vital Signs (BP, PR, SaO ₂) Confirmation of recovery from ketamine ^{2,3} 240 mL fluid intake	¹ a minimum of 60 min of recovery follow up ² as per Criteria of recovery from ketamine ³ lunch will be served after confirmation of recovery
10:00	18:00	Questioning for AEs Vital Signs (BP, PR)	dinner will be served in the evening
24:00 ¹	08:00 ¹	Questioning for AEs Vital Signs (BP, PR) 12-lead ECG C-SSRS 'since last visit' DSST, MOAA/S, CADSS, SFST Targeted Physical Examination ² Discharge from trial site ^{3,4}	¹ Day -20 to -1 at V2. The time is approximate; the procedures to be performed and completed \pm 2 h. ² incl. skin inspection for signs of rash, check for lymphadenopathy and neurological examination ³ after confirmation of fitness by the investigator ⁴ breakfast will be served before discharge

* planned time 0:00 at *Screening Ketamine Challenge (V2)* should equal planned time 0:00 relative to *Drug administration (I)* on *Day 1 (V3, V4 and V5)*.

Proprietary confidential information © 2021 Boehringer Ingelheim International GmbH or one or more of its affiliated companies

FLOW CHART D (TREATMENT KETAMINE CHALLENGE)

Day 1 of each Treatment Period (Visits 3, 4 and 5)

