3.3 SELECTION OF TRIAL POPULATION

It is planned that 36 healthy male subjects will enter the study. They will be recruited from the trial site's participant database and other means, such as advertisement pre-approved by the Institutional Review Board.

Only CYP2C19 non-poor metabolisers will be included in the trial in order to minimize potential impact on the study endpoints due to the known higher exposure of BI 409306 in CYP2C19 poor metabolisers, and minimize the safety risks related to this as well (see Section [1.2.1.4](#) and the current version of the IB [[c01694347](#)]). CYP2C19 status must be

Proprietary confidential information © 2021 Boehringer Ingelheim International GmbH or one or more of its affiliated companies

known prior to the ketamine challenge at screening in order to avoid exposure of non-eligible subjects to ketamine.

██████████ subjects performing within the normative range on CANTAB PALTEA28 at screening will be put forward for evaluation of ketamine response. Subjects will identify as normative if they perform within 2 SD of an age matched normative sample at Visit 1 and Visit 2 prior to ketamine infusion. The CANTAB software will use detailed normative data and compare each recruited participant against it. At the end of each screening session, a report will be available for download that will indicate whether the subject is eligible to proceed to ketamine challenge.

Only subjects who demonstrated response to ketamine at the selected dose/regimen at the screening ketamine challenge (Visit 2) will be included in the trial in order to increase study sensitivity. Response to ketamine is defined as a change of ≥ 10 errors on CANTAB PALTEA28 from baseline (pre-ketamine) to ketamine challenge (on ketamine). A change of 10 or more errors on PALTEA28 is equivalent to a 1 (between subjects) SD change in performance. This threshold for change will allow sufficient variability for evaluating attenuation of ketamine-induced cognitive deficits between the study treatment arms.

A log of all subjects enrolled into the trial (i.e. who have signed informed consent) will be maintained in the ISF irrespective of whether they have been treated with investigational drug or not.

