The characteristics of the challenge agent are given below:

Substance: **Ketamine hydrochloride**
Pharmaceutical formulation: injection solution
Source: [REDACTED],
[REDACTED] (or equivalent)

Proprietary confidential information © 2021 Boehringer Ingelheim International GmbH or one or more of its affiliated companies

Unit strength:	500 mg/10 mL (administered as a bolus of 0.26 mg/kg over 1 min, followed by continuous infusion of 0.0073 mg/kg/min over 89 min (reduced by 10% (or 0.00073 mg/kg/min) every 15 min)
Posology:	X**-0-0 at SCR Visit 2 X**-0-0 on Day 1 of Treatment T1 X**-0-0 on Day 1 of Treatment T2 X**-0-0 on Day 1 of Treatment T3 X**-0-0 on Day 1 of Treatment R
Route of administration:	i.v.
Duration of use:	90 min infusion***, consisting of a bolus over 1 minute, followed by continuous infusion over 89 minutes at SCR KET, and in treatments T1, T2, T3 & R

** tablets of lamotrigine have imprint "ZC 80" on one side whereas matching placebo do not have it. To ensure double-blind conditions, an eye blinding mask will be used by subjects each time during the study drug administration, and unblinded staff will be involved in dispensing and administration of the study drug.*

*** ketamine to be administered intravenously 5h after administration of BI 425809 or placebo and 2h after administration of BI 409306 or lamotrigine or placebo.*

**** infusion can be prolonged for a maximum of 15 min, i.e. to 105 min in total, in case of delays from the planned time of the assessments on ketamine, or terminated earlier if the planned assessments on ketamine are completed or any test drops out.*

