4.1.4 Drug assignment and administration of doses for each subject

This trial is a 3-way crossover study with 4 treatment arms (see Table [4.1.4: 1](#)).

At screening, all subjects will undergo a ketamine challenge receiving ketamine infusion as a bolus of 0.26 mg/kg over 1 min, followed by continuous infusion of 0.0073 mg/kg/min over 89 min (reduced by 10% every 15 min). Only those subjects who demonstrated response to ketamine, as well as confirmed their eligibility in accordance to the other inclusion and exclusion criteria indicated in Sections [3.3.2](#) and [3.3.3](#), will be included in the study, and will receive 3 treatments: each subject will be randomly allocated to one of the 18 3-period sequences including placebo in one of the periods and 2 out of the 3 active treatments (T1, T2 and T3) in the remaining periods.

Administration of *BI 425809 or placebo* will be performed 5 h prior to ketamine infusion, after subjects had a light breakfast (e.g. a muffin with a glass of juice), which will be served 30 min before the drug administration.

Administration of *lamotrigine or BI 409306 or placebo* will be performed 2 h prior to ketamine infusion, after subjects had a light snack (clear liquid) (e.g. one or two cups of gelatin or a popsicle), which will be served approximately 5 min before the drug administration.

Before administration, the study drug will be dispensed into the individual subjects’ dispensing bottles by the unblinded pharmacists. The unblinded nurses will administer the trial medication as oral doses each time together with about 240 mL of water to subjects who are in a sitting position. During administration of *lamotrigine or BI 409306 or placebo* in each treatment period, subjects will wear an eye blinding mask. For drug administration, the so-called four-eye principle (two-person rule) should be applied. For this, one unblinded authorised employee of the trial site should witness the administration of trial medication, and its dispensing.

Proprietary confidential information © 2021 Boehringer Ingelheim International GmbH or one or more of its affiliated companies

Table 4.1.4: 1 Dosage and treatment schedule

Treatment	Substance	Formulation	Unit strength	Dosage	Total dose
T1 (Test 1)	Lamotrigine	Tablet	100 mg	3 tablets once 2h prior to ketamine infusion	300 mg
Lamotrigine Treatment	Placebo to [REDACTED] BI 409306	Tablet	N/A	1 tablet once 2h prior to ketamine infusion	N/A

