SCR BL will be done first followed by SCR KET, as indicated in the [Flow Chart](#). Only subjects that show [REDACTED] will be allowed to enter the trial.

[REDACTED]. A change of 10 or more errors on PALTEA28 is equivalent to a 1 SD (between subjects) change in performance. This will allow ample variability to evaluate attenuation of k [REDACTED] between treatment arms. An indication of whether a participant should be screened out due to absence of [REDACTED] will be provided through the CANTAB software as a downloadable report and will be available following completion of the CANTAB assessments.

The assessments of SCR KET will also be used as baseline for the assessments performed on the test days of the treatment periods, i.e. under treatments T1, T2, T3 and R. Therefore, it is of upmost importance that SCR KET assessments will be performed time-matched, i.e. exactly at the same time of the day, to the later assessments under treatments T1, T2, T3 and R.

Recovery from ketamine must be confirmed via criteria of recovery from ketamine. Recovery follow up can be terminated after a minimum of 60 minutes when all applicable recovery criteria are met (see Section [5.2.5.6](#)).

During and after assessments subjects are kept under close medical surveillance for at least 5 h after stop of the ketamine infusion. The subjects will then be allowed to leave the trial site after successful completion of the discharge assessments (incl. C-SSRS; DSST, MOAA/S, CADSS, SFST), formal assessment and confirmation of their fitness. Discharge will be postponed if subjects fail to pass C-SSRS, DSST, MOAA/S, CADSS and/or SFST or any time if deemed necessary by the investigator (for details refer to Sections [5.2.5.2](#) and [5.2.5.5](#)).

For information regarding laboratory tests (including drug and virus screening), ECG, [REDACTED] C-SSRS, vital signs, safety tests (DSST, MOAA/S, CADSS, SFST), visual acuity test and physical examination incl. targeted examination, refer to Section [5.2](#).

For details on the trial procedures related to SARS-CoV-2/ COVID-19 in context of pandemic during screening period, refer to Appendix [10.7.3.1](#).

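### The readable early-stop rule for the screening ketamine infusion does not name ineligibility, so by default a man shown at about minute 39 to be a non-responder has about 51 planned minutes left

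*Protocol*

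**What the plan says.** **Who is infused, and for how long.** Protocol Section 4.1.4 states: "At screening, all subjects will undergo a ketamine challenge receiving ketamine infusion as a bolus". It gives the full regimen and only then turns to selection: "over 89 min (reduced by 10% every 15 min). Only those subjects who demonstrated response to ketamine". Section 4.1.1 describes the duration as "consisting of a bolus over 1 minute, followed by continuous infusion over 89 minutes at SCR KET", the same as in the treatment periods.

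**When the result is known.** In Flow Chart C the infusion starts at 13:00. The on-ketamine PAL starts at 13:27, with a review of the inclusion and exclusion criteria in the same row and the eligibility result shown when PAL ends. The next row is 13:39. Redacted assessments run from 13:40, and the stop is planned for 14:30. A PALTEA28 change below 10 errors is exclusion criterion 25 (Section 3.3.3).

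**When the infusion may end early.** The comment on the 14:30 row of Flow Chart C reads "or terminated earlier, if the above tests are completed (or any test drops out". The footnote in Section 4.1.1 reads "or terminated earlier if the planned assessments on ketamine are completed or any test drops out", and the Synopsis footnote says the same. The early-stop clause ends without redaction in all three places. It is followed by blacked-out text in footnote 12 of Flow Chart A and in Sections 4.1.2 and 6.1.

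**What happens between tests.** Footnote 8 of Flow Chart A and Section 6.1 ask staff to keep gaps short during the infusion. When one test finishes early or is dropped, they are to move directly to the next.

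**Purpose of the session.** Section 6.2.1 uses it to establish response, and adds: "The assessments of SCR KET will also be used as baseline for the assessments performed on the test days of the treatment periods".

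**The concern.** These are healthy volunteers, and Section 1.4 states that they gain no therapeutic benefit. Once PAL shows a change below 10 errors the man cannot be enrolled. Neither readable use of the session still applies to him: the response question is settled, and he will have no treatment periods for which to supply a baseline. The treated set and the pharmacodynamic set both require randomisation (Protocol Section 7.2.1, SAP Section 6.3), so he belongs to neither. No readable text says that the infusion then stops.

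The earlier checks are firmer. Flow Chart B lets testing go on only if the man remains eligible. For the pre-ketamine PAL, Section 3.3 says "a report will be available for download that will indicate whether the subject is eligible to proceed to ketamine challenge". For the on-ketamine PAL the only readable consequence is that he is not included in the study (Section 3.1) or is screened out (Section 6.2.1).

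What is at stake is avoidable exposure to a drug for which Section 1.2.4.3 lists blood-pressure, respiratory and psychiatric reactions. Nothing in the estimate or its precision is at stake.

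**Working it through.** **Inputs.** Clock times come from Flow Chart C: start 13:00, row after PAL 13:39, stop 14:30. Section 4.1.2 gives the dose: bolus 0.26 mg/kg over 1 min, then 0.0073 mg/kg/min for 89 min, cut by 10% (or 0.00073 mg/kg/min) every 15 min, with prolongation to at most 105 min.

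**The plan's own figures.**
- 14:30 − 13:00 = 90 min, and 1 + 89 = 90 min.
- 0.0073 × 89 = 0.6497 mg/kg, the stated 0.65 mg/kg before the taper.
- Both are reproduced.

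**Time left after the result.**
- Result known: 13:39 − 13:00 = minute 39.
- Remaining: 14:30 − 13:39 = 51 min, and 51/90 = 57% of the infusion time.
- If prolonged to the maximum: 105 − 39 = 66 min.

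**Dose left, fixed cut of 0.00073 every 15 min, steps counted from minute 0.**
- Infusion, minutes 1–90: 14 × 0.0073 + 15 × (0.00657 + 0.00584 + 0.00511 + 0.00438 + 0.00365) = 0.1022 + 0.3833 = 0.4855 mg/kg.
- Session total: 0.26 + 0.4855 = 0.7455 mg/kg.
- Minutes 39–90: 6 × 0.00584 + 15 × (0.00511 + 0.00438 + 0.00365) = 0.0350 + 0.1971 = 0.2321 mg/kg.
- Share: 0.2321/0.7455 = 31%.

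**Sensitivity.**
- Steps counted from minute 1: total 0.7491, remaining 0.2343 mg/kg, again 31%.
- 10% read as a proportional cut of the current rate: total 0.766–0.769, remaining 0.252–0.253 mg/kg, 33%.

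**Stop routes in the readable text, set against a non-responder who is otherwise well.**
- Assessments completed: not met at 13:39, because tests are scheduled from 13:40.
- A test drops out: met only if someone decides to drop his tests. Footnote 8 and Section 6.1 also say that a dropped test leads to the next one.
- Safety reasons or the man's own request (Sections 3.3.4.1 and 4.1.2): not triggered by non-response.
- Investigator's clinical judgment (Section 3.3.4.1): available, but written under discontinuation of trial treatment. It permits a stop without calling for one.

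On the readable text, the default is therefore that the infusion runs on.

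**The case against.** The strongest reply is that the gap is a missing sentence, not an instruction to continue. Flow Chart C puts an eligibility review exactly where it is needed, and a review placed mid-infusion is most naturally a decision point. Section 6.2.1 speaks of screening the man out. His remaining tests can then be dropped, and Section 4.1.2 says the infusion is to end early in that case. This stands to the extent that a sensible site can stop. It does not show that every site will, because the only written direction after a completed test is to start the next one.

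A second reply is redaction. The same rule runs into blacked-out text in footnote 12 and Sections 4.1.2 and 6.1, the response rule in Section 6.2.1 is partly blacked out, and so are the 13:40–14:30 assessments. This also stands: an instruction may exist there, and a use for the later recordings cannot be ruled out. If there is an instruction, the Synopsis, Section 4.1.1 and Flow Chart C, which is the bedside schedule, still do not carry it.

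A third is that the risk is limited. The bolus is already in, the rate is tapering, oxygen saturation and ECG are monitored continuously, and the man may end the infusion at any time (Section 1.4). That lowers the risk but does not make the exposure useful.

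**Conclusion.** On the readable text the point holds as an inexpensive safety improvement. A man found to be a non-responder has by default about 51 planned minutes of infusion left, about 0.23 mg/kg or 31% of the session dose (33% if the taper is proportional). This assumes that the planned times are kept, that the result is read when PAL ends, and that no redacted instruction says otherwise.

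Four stronger readings might be inferred, and the documents do not support them.
- *The protocol orders non-responders to be kept on ketamine.* It does not. It is silent, and it leaves room to stop.
- *It breaks its own stated aim.* Section 3.3 does say "known prior to the ketamine challenge at screening in order to avoid exposure of non-eligible subjects to ketamine", but of CYP2C19 status, which can be established beforehand. Non-response can be found only by giving ketamine. Applying the same reason to the minutes after PAL is sensible, but it is an inference.
- *The number of men can be worked out from Section 7.5.* It cannot. The SDs in Table 7.5:1 are for placebo-minus-drug differences, not for individual ketamine-induced changes. The 4 to 6 errors are not paired with 30% and 50%, so the implied mean deficit could be anywhere from 4/0.50 = 8 to 6/0.30 = 20 errors. No response rate is given.
- *The trial's result is affected.* It is not. Non-responders are never randomised.

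**What to change.** Add to the 13:27 row of Flow Chart C and to Section 6.2.1: *If the PALTEA28 change is <10 errors, omit the remaining tests, stop the infusion and follow the recovery procedures.*

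Add to the early-stop rule: *or the subject is found ineligible at SCR KET*. The places are the Synopsis footnote, the 14:30 comment in Flow Chart C, footnote 12 of Flow Chart A, and Sections 4.1.1, 4.1.2 and 6.1. If a redacted passage already says this, only the Synopsis, Section 4.1.1 and Flow Chart C need to be brought into line.

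The cost is one sentence and one trigger, through an amendment. No procedure, staff or subjects are added. The result is already displayed, but someone must read it before the 13:40 test begins. The 13:40–14:30 recordings in non-responders are lost, which matters only if a redacted analysis uses them.
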